All patients randomised who receive the first treatment will be included in the intention-to-treat analysis of primary endpoint. Prior to the first treatment, it was anticipated that some patients (up to 10%) would fail to attend after eligibility was assessed due to a failure of compliance with the travel and attendance needs of the treatment course or study. These were not counted as study recruits. Those in whom post-treatment data are unavailable at 14 weeks for any reason (loss to follow up, failure to complete treatment) will have their outcome multiply imputed under the assumption of missing at random (MAR) using variables prognostic of outcome, such as measure of outcome made at baseline, and others that are predictive of missingness such as mean number of FI episodes per week at baseline, age, sex, and where available, mid-study bowel diary data. See appendix (b) for details. Multilevel multiple imputation will be performed using the multivariate normal distribution in Realcom Impute, using treatment allocation, patient sex and allocation as auxiliary variables. After a burn in of 1,000 runs of the MCMC sampler, missing values will be filled every 500th run to create a total of 10 completed datasets for analysis. The data will be analysed in Stata and the results pooled by Rubin's rules.

Method for handling centre effects

Study centre will be included as a random effect

Method for handling randomisation stratification or minimisation factors

Patient sex will be included as a fixed effect, study centre as a random effect

Method for handling clustering effects

The intraclass correlation coefficients (ICC) and their 95% confidence intervals for the outcomes by centre (level 2) will be estimated using the user-contributed Stata command *sea_obi* which allows the ICC to be negative. Random effects models will be fitted by restricted maximum likelihood estimation (e.g. *xtmixed ...*, *reml*). However, should these fail due to the between centre variance being close to zero, random effects models will be fitted by generalised least squares (e.g. *xtregress*). If ICCs are estimated as ≤ 0 then we will use similar regression models without adjusting for clustering.

Method for selecting other variables that will be adjusted for

This was agreed by consensus prior to any data extraction and the decision was: fit fixed effects for sex, randomisation and baseline level of outcome.

Multiple comparisons and multiplicity

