The PTNS treatment and sham have no recognised significant adverse effects. However, at each weekly visit each patient will be asked if they have suffered any side effects or adverse effects of the treatment. These will be documented and in the study database and reported to the data monitoring committee prior to each meeting with them.

Adverse events leading to withdrawal

Serious adverse events

Clinical laboratory evaluations

SUBGROUP ANALYSES

Definition of outcome measure

Definition of subgroups

Primary outcome –

Sex (male vs. female)

FI severity ($<$ or \geq 7 episodes/wk)

Secondary outcomes –

age (<40 years, 40 to 60 years, 60+ years),

Sample size justification for the subgroup analysis

None

Descriptive analysis for subgroups

Method of analysis

An interaction term will be defined by multiplying the sub group dummy variables by the treatment assignment variable. For age, a global test of the two interaction terms will be performed using a likelihood ratio test.

AMENDMENTS TO VERSION 1.0

The pre-planned subgroup analysis ‘urge versus passive FI episodes’ had been inadvertently left out of version 1.0.

- Further, the sub-group analyses were to be conducted only on the primary outcome and not on the secondary outcomes as previously written.
- The Stata code listed in appendix 14(a) was refined during the analysis to correctly handle patients with fewer than 7 days of bowel diary data and the new code has replaced that previously in 14(a). The code to define stool consistency outcomes was not included in version 1.0 and was developed during the analysis.
- The listing of variables used in the multilevel multiple imputations was updated during the analysis to include more detail and also the imputation model for the four binary outcomes (primary (\geq 50% reduction in FI) and three secondary (\geq 25%, \geq 75%, 100%)).

REFERENCES

Kahan BC & Morris TP. Analysis of multicentre trials with continuous outcomes: when and how should we account for centre effects? *Statist. Med* 2013, 32 1136–1149

APPENDICES

Stata code for creating outcome variables

*** Bowel diary data

```
forvalues i = 1(1)14 {
replace Q3_`i' = "" if Q3_`i' == "."
encode Q3_`i', generate(x)
drop Q3_`i'
rename x Q3_`i'
recode Q3_`i' (1=0) (2=1)
label variable Q3_`i' YN

replace Q4a_`i'="" if Q4a_`i' == "."

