replace FI1_rev=2 if FI1==4
replace FI1_rev=3 if FI1==3
replace FI1_rev=4 if FI1==2
replace FI1_rev=5 if FI1==1

egen FIQoL_lif = rowmean(FI2a FI2b FI2c FI2d FI2e FI2g FI2h FI3b FI3l
FI3m)
egen FIQoL_cop = rowmean(FI2f FI2i FI2j FI2k FI2m FI3c FI3h FI3j
FI3n)
egen FIQoL_dep = rowmean(FI1_rev FI3d FI3f FI3g FI3i FI3k FI4)
egen FIQoL_emb = rowmean(FI2l FI3a FI3e)

egen mFIQoL_lif = rowmiss(FI2a FI2b FI2c FI2d FI2e FI2g FI2h FI3b
FI3l FI3m)
egen mFIQoL_cop = rowmiss(FI2f FI2i FI2j FI2k FI2m FI3c FI3h FI3j
FI3n)
egen mFIQoL_dep = rowmiss(FI1_rev FI3d FI3f FI3g FI3i FI3k FI4)
egen mFIQoL_emb = rowmiss(FI2l FI3a FI3e)

replace FIQoL_lif =. if mFIQoL_lif ~= 0
replace FIQoL_cop =. if mFIQoL_cop ~= 0

```

```
replace FIQoL_dep =. if mFIQoL_dep ~= 0
replace FIQoL_emb =. if mFIQoL_emb ~= 0
```

Variables to be used in the multilevel multiple imputation

Outcomes that are reported as a group of domains will be imputed together where possible. Baseline measures, mid-treatment (bowel diary data only) and end of treatment outcomes will be included together in the multivariate response. Centre is the only level 2 variable (random intercepts)

Outcomes	Imputation Variables	
	To include in multivariate response	Auxillary variables
Mean number of FI episodes per week	Mean number of FI episodes per week, St Mark's Continence Score, Likert	Age, Sex and random allocation
GI QOL Index (reported as total score)	Mean number of FI episodes per week, St Mark's Continence Score, GI QOL	Age, Sex and random allocation
Patient centered outcomes form	Patient centered outcomes form	Age, Sex and random allocation
SF-36 (eight domains)	SF-36 (4 domains at a time)	Age, Sex and random allocation
Quality of life scale for FI (four domains)	QOL for FI	Age, Sex and random allocation
St Marks Continence Score	Mean number of FI episodes per week, St Mark's Continence Score	Age, Sex and random allocation
EQ-5D	EQ-5D	Age, Sex and random allocation

List of case report forms (see statistics master file for detail)

- CRF 1 – Eligibility assessment
- CRF 2 – Initial assessment
- CRF 3 – PRE-TREATMENT questionnaires
- CRF 3 – POST-TREATMENT questionnaires
- CRF 4 – Randomisation
- CRF 5 – Record stimulation parameters adverse events and medication / pad usage
- CRF 6 – Post-treatment information
- CRF 7 – Final study visit information
- BOWEL DIARY – PRE-TREATMENT (14 days)
- BOWEL DIARY – MID-TREATMENT (7 days)
- BOWEL DIARY – POST-TREATMENT (14 days)

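### The listed imputation models contain no treatment-by-covariate term, so the planned subgroup interaction tests, if run on the imputed data, are pulled towards no interaction

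*SAP*

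**What the plan says.** **Imputation.** The SAP section on withdrawals, loss to follow-up and missing data covers "Those in whom post-treatment data are unavailable at 14 weeks for any reason". It states: "Multilevel multiple imputation will be performed using the multivariate normal distribution in Realcom Impute". The auxiliary variables are given there by the words "using treatment allocation, patient sex and allocation as auxiliary variables", which name allocation twice and leave out age. The appendix table of imputation variables gives "Age, Sex and random allocation" in every row, with centre as a random intercept. It adds: "Baseline measures, mid-treatment (bowel diary data only) and end of treatment outcomes will be included together in the multivariate response". The sampler is run "to create a total of 10 completed datasets for analysis", which are pooled by Rubin's rules.

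**Subgroups.** The section on subgroup analyses lists sex, FI severity (split at 7 episodes per week) and age. The amendments section restores urge versus passive FI and confines subgroup analyses to the primary outcome. The method is: "An interaction term will be defined by multiplying the sub group dummy variables by the treatment assignment variable".

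**Other datasets.** The available-case population and the sensitivity analyses for the primary outcome are both marked as not applicable.

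**The concern.** An imputation model should allow at least the associations that the analysis model will test. Here the listed models hold allocation, sex and age as plain covariates. Baseline FI shares one covariance structure across both arms, so its slope is also common to both. Urge/passive type is not listed even as a main effect. The subgroup models then ask whether the treatment effect differs by these same factors. Imputed patients contribute little or no interaction, apart from what a mid-treatment diary carries.

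The harm is one of interpretation. A real difference in PTNS effect by severity or sex would be understated and more often missed. A null interaction test could then be read as evidence of a uniform effect when the imputation partly produced it.

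**Working it through.** **The plan's own figure.** For 55% v 35% at 80% power and two-sided 5%, the two-proportion formula gives 96 per arm (192) without continuity correction and 106 per arm (212) with it. This matches the stated 212. Then 212 / 0.90 = 235.6, against a stated target of 235. These figures concern the main comparison. The SAP gives no sample size justification for the subgroup tests.

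**Inputs.** From the SAP: 227 randomised 1:1, about 10% male, 10 imputations, Rubin's rules, two-sided 5%. Assumed: 5%, 10% or 20% of 14-week outcomes missing at random. The 10% in the SAP is non-attendance before first treatment, not missing outcomes.

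**Why the estimate shrinks.** Let f be the missing fraction, equal across the four treatment-by-subgroup cells, and δ the interaction among observed patients. After imputation each cell mean is (1 − f) × observed mean + f × fitted mean. Fitted means from an additive model have zero interaction contrast, so the completed-data contrast is (1 − f)δ + f × 0 = (1 − f)δ.

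**Simulation, continuous scale, unit residual SD.** The true interaction was set to give about 80% power with complete data. For a 50/50 split the standard error is 4/√227 = 0.2655, so δ = 2.80 × 0.2655 = 0.744. For a 10% subgroup it is 2/√(227 × 0.1 × 0.9) = 0.4425, so δ = 1.24. The table shows the mean estimate after additive imputation divided by the complete-data estimate. The mid-diary columns assume that every missing patient has a mid-treatment diary, with correlation 0.6.

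| Missing | 1 − f | 50/50, no mid diary | 10% subgroup, no mid diary | 50/50, mid diary | 10% subgroup, mid diary |
|---|---|---|---|---|---|
| 5% | 0.95 | 0.705/0.742 = 0.95 | 1.171/1.239 = 0.95 | 0.729/0.748 = 0.97 | 1.205/1.236 = 0.97 |
| 10% | 0.90 | 0.668/0.740 = 0.90 | 1.105/1.235 = 0.89 | 0.714/0.752 = 0.95 | 1.168/1.235 = 0.95 |
| 20% | 0.80 | 0.577/0.723 = 0.80 | 0.977/1.236 = 0.79 | 0.657/0.736 = 0.89 | 1.147/1.282 = 0.89 |

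With the treatment-by-subgroup term in the imputation model the bias disappears (50/50, no mid diary: 0.743, 0.744 and 0.725 at 5%, 10% and 20%).

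**Power, additive imputation v imputation with the interaction.**
- 50/50, no mid diary: 74% v 77% (5% missing), 66% v 74% (10%), 47% v 66% (20%). Observed patients only: 77%, 75% and 67%.
- 10% subgroup, no mid diary: 62% v 70% (10%), 47% v 65% (20%).
- 50/50, mid diary in all: 72% v 76% (10%), 63% v 70% (20%).

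**No true interaction (no mid diary).** Additive imputation rejects in 2.7% (10% missing) and 1.3% (20%) of trials, instead of 5%.

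**Responder scale.** In a large-sample run of 2,000,000 patients with the binary outcome imputed directly, the log odds ratio for the interaction kept 0.95, 0.90 and 0.80 of its value for both sex and severity. Deriving the responder from an imputed FI count instead gave, for severity, 0.715/0.795 = 0.90 at 10% and 0.639/0.795 = 0.80 at 20%. With no true interaction, count imputation created none.

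**A second responder-scale simulation** (odds ratio 1.3 if mild, 4.0 if severe; missingness depending on arm and baseline FI; no mid diary) gave complete-data log odds ratio 1.15 and power 51%. Additive imputation gave 1.02 and 38% at 10% missing, and 0.87 and 21% at 20%. The attenuation is 1 − 1.02/1.15 = 11% and 1 − 0.87/1.15 = 24%. Imputing by arm gave 1.11 and 42%, then 1.05 and 34%. Observed patients gave 47% and 41% power.

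**The case against.** **The functional form is inferred.** The SAP lists variables, not model terms, and does not say in words whether the arms are imputed jointly. The amendments section says an imputation model for the four binary outcomes was added to the listing, but the table as it can be read has no such row; the row may have been lost in conversion. The model that feeds the subgroup tests may therefore not be visible. This stands, and it makes the point conditional. Following the variables as listed, though, gives an additive model.

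**Use of imputed data is not stated.** The subgroup section does not name a dataset, and the likelihood ratio test specified for age is not pooled directly by Rubin's rules. The status of age is itself unclear: the subgroup section lists it under secondary outcomes, while the amendments section confines subgroups to the primary outcome. This also stands, but the SAP offers no other dataset.

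**A reader might infer that missing outcomes are filled in as if PTNS worked equally in everyone.** That is too strong. The mid-treatment diary, where available, is in the imputation and carries part of any interaction; it roughly halves the shrinkage.

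**A reader might infer that imputing by arm is the required cure.** The figures do not support that. About 227/2 × 0.10 ≈ 11 males per arm, and 113.5/19 ≈ 6 patients per arm and centre, leave thin data. In the second simulation by-arm imputation had less power than observed patients alone.

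**The consequence is limited.** The subgroup tests are not powered by design, and the error is conservative.

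**Conclusion.** The point holds in conditional form. If the subgroup tests use data imputed from the models as listed, interaction estimates shrink by roughly the missing fraction: about 5%, 10% and 20% at those missing rates, and about half that with a mid-treatment diary. The tests lose power and become conservative. The size rests on an assumed missing rate: it is small at 5% and material at 20%.

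A reader might go further and infer that the main trial result is biased, or that spurious subgroup effects will appear. Neither is supported. The primary model has no interaction term, and the null rejection rate falls below 5% rather than rising above it. This is a secondary matter, but it goes beyond missing detail, because following the listed models biases planned tests in a known direction.

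**What to change.** 1. For the subgroup analyses, add to the imputation model the product of treatment with sex, severity and urge/passive type (with its main effect), and with age if that subgroup is retained. Alternatively, impute separately by arm where numbers allow.
2. Make sure that the appendix table shows the row for the binary outcomes with its terms, and bring the auxiliary variables in the missing-data section into line with the table.
3. State which dataset the subgroup tests use and how the age test is pooled.
4. Report the same subgroup tests on observed patients as a sensitivity analysis.

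The cost is a few lines of text, one extra imputation run and slightly larger imputation variance. The sex terms will remain imprecise because only about 10% of patients are male. The imputation for the primary comparison can stay as it is.

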HEALTH TECHNOLOGIES BEING ASSESSED: PTNS (Urgent ® PC neuromodulation system) is produced by a single manufacturer (Uroplasty ®). The equipment includes a hand held pulse generator unit, single use leads and fine needle electrodes. Needle insertion is performed in a sitting position in an outpatient setting on either leg adhering to the manufacturer's protocol (and specialist training). Treatment is for 30 mins. weekly for a duration of 12 weeks. Validated sham stimulation - insertion of the Urgent PC needle subcutaneously at the same site with electrical stimulation delivered to the distal foot using TENS.

MEASUREMENT OF COSTS AND OUTCOMES: Primary outcome variable: change in weekly FI episodes (calculated from bowel diaries) expressed as proportion of patients achieving $\geq 50\%$ reduction in FI episodes per week; Secondary outcomes: (1) percentage change in FI episodes per week, (2) change in mean number of FI episodes per week, (3) validated patient-rated quantitative outcomes including symptom severity score (St Mark's score), disease-specific: FI-QOL, and generic: EQ-5D QOL measures, and SF-36, (4) FI-specific patient-centred outcomes (5 validated key issues), (5) Likert scales of patient's global impression of success (0-10), (6) Short urinary symptom assessment. Adverse events and anti-diarrhoeal drug usage will also be recorded. Economic analysis will measure direct NHS costs with utilities derived from the EQ-5D. The proposed HE analysis will be detailed in a separate document.

Changes from planned analysis in the protocol

We decided to fit random centre effects rather than fixed effects on the basis of findings by Kahan & Morris (Kahan & Morris, 2013). We also decided to multiply impute the data and remove any reference to last observation carried forward.

STUDY OBJECTIVES AND ENDPOINTS

Study objectives

Primary objectives

To determine the effectiveness of PTNS versus sham electrical stimulation based on changes in the number of weekly FI episodes from baseline (bowel diary completed over two week period prior to first intervention) to end of treatment (bowel diary completed for weeks 12 and 13)

Secondary objectives

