Short urinary symptom assessment (descriptive)

Change in medication use: has pad usage/loperamide usage decreased/remained the same/increased? (descriptive)

Safety outcomes

None

STUDY METHODS

Overall study design and plan

Target for analysis: 106 intervention and 106 sham participants

Actual number randomised: 227

Date of first randomisation: 21/01/2012

Date of last randomisation: 31/10/2013

Trial design: individually randomised, parallel group

Blinding: See section 3.4

Randomised Interventions: PTNS vs. sham

Allocation ratio: 1:1

Selection of study population

Inclusion Criteria

Faecal incontinence sufficiently severe enough to warrant intervention

Failure of appropriate conservative therapies

Age \geq 18 years

Exclusion Criteria

Inability to provide informed consent for the research study

Inability to fill in the detailed bowel diaries required for outcome assessments (this will exclude participants who do not speak / read English)

Neurological diseases, such as diabetic neuropathy, multiple sclerosis and Parkinson's disease (any participant with painful peripheral neuropathy)

Anatomical limitations that would prevent successful placement of needle electrode

Other medical conditions precluding stimulation: e.g. bleeding disorders, certain cardiac pacemakers, peripheral vascular disease or ulcer, lower leg cellulitis

Congenital anorectal anomalies or absence of native rectum due to surgery

A cloacal defect

Present evidence of external full thickness rectal prolapse

Previous rectal surgery (rectopexy / resection) done < 12 months ago (24 months for cancer),

Stoma *in situ*

Chronic bowel diseases such as inflammatory bowel disease leading to chronic uncontrolled diarrhoea

Pregnancy or intention to become pregnant

Previous experience of SNS or PTNS

Method of treatment assignment and randomisation

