Age, sex, history of faecal incontinence (including type), urinary symptom history, previous faecal incontinence treatments, medications, past medical history, past obstetric history. (see CRF 2 v5 for items)

Bowel diary (14 consecutive days)

Gastrointestinal quality of life index, patient centred FI symptoms, SF-36 Health Survey, QoL scale for faecal incontinence, St. Mark's faecal incontinence score, EQ-5D health questionnaire (see CRF 3 v3 for detail)

Follow up

Visits 2-13: PTNS or tens machine settings and response (sensory or motor), adverse events, any change in pad usage, any changes in medication use? (see CRF 5 v3)

Week 7: bowel diary over 7 consecutive days

Final visit (post treatment) (week 14): which treatment did patient think they were on?

Any effect on urinary symptoms? Any change in loperamide or codeine use? Any change in pad use? How patient felt before, during and after treatment, Likert scale of success.

Bowel diary over 14 consecutive days

CRF 3 v3

Timing of data collection

Event	Visit 1	Telephone Conversation	Visit 2	Visits 3-13	Visit 14
Eligibility assessment	X				
Bowel Diary		X		Visit 7-8	X
Consent			X		
Participant Contact Information Sheet			X		
Eligibility assessment (CRF1)			X		
Initial assessment (CRF2)			X		
Questionnaires (CRF3)			X		X
Randomisation			X		
Randomisation information (CRF4)			X		
Intervention			X	X	
Record stimulation parameters adverse events and medication / pad usage (CRF5)			X	X	
Adverse Events Log			X	X	X
Concomitant Medications Log			X	X	X
Post treatment Information (CRF6)					X
Final Study Visit Information (CRF7)					X

GENERAL ISSUES FOR STATISTICAL ANALYSIS

All analyses will be conducted two sided and significance interpreted at the 5% level.

Blinding of the statistical analysis

The trial statistician will remain blind to allocation until this analysis plan was signed off

Analysis populations

Intent-to-treat population

The intention-to-treat (ITT) sample is defined for this trial as all participants randomised into the trial, *who received at least their first treatment*, included in the intervention group to which they were randomised.

Available-case population

N/A

Per protocol population

Patients attending at least 10 treatment sessions in 13 weeks will be classed as treatment completers.

Safety population

N/A

Other populations

N/A

Database

Description

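### Adverse events are collected throughout treatment, but the SAP sets safety outcomes to None and plans no by-arm harm summary for the principal paper

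*SAP*

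**What the plan says.** Under Outcome measures, the heading "Safety outcomes" is followed by None. Under Analysis populations, the heading "Safety population" is followed by N/A. In Safety and tolerability analyses, intervention exposure is also N/A.

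The text under All adverse events opens with a premise: "The PTNS treatment and sham have no recognised significant adverse effects". It then has each patient asked about side effects at each weekly visit, and says of the answers: "These will be documented and in the study database and reported to the data monitoring committee prior to each meeting with them". The next two headings, for adverse events leading to withdrawal and for serious adverse events, have no text under them.

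The data collection is fuller than this. The Summary, in its paragraph on costs and outcomes, says: "Adverse events and anti-diarrhoeal drug usage will also be recorded". The Follow up list has "Visits 2-13: PTNS or tens machine settings and response (sensory or motor), adverse events, any change in pad usage". In the Timing of data collection table, the row "Adverse Events Log" is marked for visit 2, visits 3-13 and visit 14.

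**The concern.** The SAP says in its Introduction that it sets out the analyses and results to be reported in the principal paper(s). It has its own safety section. An entry of None there is therefore a statement about what the paper will contain. It is not a detail handed to the protocol.

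That statement sits badly with the rest of the document. The Summary names adverse events and anti-diarrhoeal drug use in the same sentence as things to be recorded. Drug use then appears among the secondary outcomes as a descriptive item, while adverse events get no outcome, no denominator and no summary.

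The stated reason is a prior belief that neither PTNS nor sham has important adverse effects. A randomised sham-controlled trial can put that belief beside data, and this plan does not ask for it.

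Two things are at stake. A reader weighing whether to offer PTNS needs harm alongside benefit. Also, the Introduction requires unplanned analyses to be identified as such, so a by-arm table added later would carry that label, with categories and denominator chosen after unblinding. Under Treatment masking, the staff member who gives the treatments is unblinded, and adverse events are recorded at those consultations. That is a further reason to fix the categories beforehand.

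**Working it through.** The plan gives no adverse event rate and no safety figure, so there is nothing of its own to reproduce on this point. The check is a reading of every place where a by-arm harm result could come from, followed by a calculation for scale.

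**Step 1. Where a by-arm harm result might come from**

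| Place in the SAP | What it provides | By-arm harm result? |
|---|---|---|
| Outcome measures, safety outcomes | None | No |
| Analysis populations, safety population | N/A | No |
| Safety section, all adverse events | Database entry and reports to the data monitoring committee | No |
| Safety section, withdrawal-related and serious adverse events | Headings without text | No |
| Comparison of losses to follow-up | Proportion withdrawing, by arm, all causes together | No, cause is not separated |
| Descriptive analyses, opening note | Descriptive statistics on all database variables, to find errors and missing data | No, it is a data check and is not stated to be by arm |
| Comparison of compliance | Distribution of sessions attended, by arm | No, but it supplies exposure by arm |

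No entry gives a count or percentage of patients with adverse events, or a count of events, by arm.

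**Step 2. Whether a denominator exists**

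The ITT population is everyone randomised who received at least the first treatment, in the arm to which they were randomised. That can serve as the safety denominator, but the SAP does not say so.

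**Step 3. Scale**

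Inputs: 227 randomised and 1:1 allocation (Overall study design and plan). Assumption: about 113 per arm, since 227 / 2 = 113.5.

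With no events among n patients, the exact upper limit for the true risk is:
- two-sided 95%: 1 − 0.025^(1/n). For n = 113 this is 3.2%.
- one-sided 95%: 1 − 0.05^(1/n). For n = 113 this is 2.6%.

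The SAP states that all analyses are two-sided, so 3.2% is the figure that matches it. With 106 per arm, the SAP's target for analysis, the limits are 3.4% and 2.8%.

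The chance of seeing at least one case in an arm of 113 is 1 − (1 − p)^113. The true risks p below are assumptions, because the SAP gives none:

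| Assumed true risk | Chance of at least one case |
|---|---|
| 1% | 68% |
| 2% | 90% |
| 5% | 99.7% |

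A simple table would therefore be informative about events of a few per cent or more, and only weakly so about rarer ones.

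The number of visit-level enquiries is at most 227 × 12 = 2,724. That assumes every patient attended every session, and it measures collection effort only.

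**The case against.** The best case for the plan has five parts.

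- **None may mean only that there is no prespecified safety endpoint.** Adverse events are still recorded and seen by the data monitoring committee. This is a fair reading of the word, but it does not supply a result. Committee reports serve oversight during the trial and are not a reported comparison.
- **Descriptive statistics are required for all variables, and adverse events are in the database.** True, but the stated purpose is to find errors, and the note does not say by arm or for publication.
- **A separate safety population is redundant.** This stands. The ITT set already requires a first treatment, so N/A is tolerable once the ITT set is named as the denominator.
- **Exposure is already covered.** This also stands. A reader might infer from the N/A under intervention exposure that sessions received will not be shown by arm. The compliance section plans exactly that comparison.
- **Seriousness, causality and coding rules usually sit in the protocol, and the CRF contents are not shown.** This stands in part. The documents do not establish that relatedness to treatment is coded, so a line for treatment-related events can only be conditional. The SAP's own headings do presuppose serious events and events leading to withdrawal as categories.

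A reader might also infer that the sponsor decided to leave harms out of the paper altogether. The document does not support that. Two of the safety headings are empty rather than marked None, which looks more like an unfilled template, and nothing bars a table that is labelled as unplanned.

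**Conclusion.** The point holds as a reporting gap. The SAP states None for safety outcomes and N/A for the safety population and leaves two safety headings without text. The only uses it states for adverse events are database entry and committee reports. No harm result by arm is planned for the principal paper(s). The conclusion rests on the None and N/A entries and on the absence of any by-arm summary elsewhere, and it would stand even if the empty headings were set aside.

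Its size is moderate. The primary estimate, type I error and power are untouched. What is lost is the planned harm side of the comparison, which at about 113 per arm could bound the risk of an event not seen in an arm at about 3.2% (exact two-sided 95%). That figure assumes near-equal arms and that essentially all of the 227 randomised received a first treatment. It would not be right to conclude that the trial lacks a usable denominator or exposure data, or that harms could not be reported at all.

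**What to change.** 1. Under Safety outcomes, replace None with a descriptive outcome, and fill the headings for all, serious and withdrawal-related adverse events accordingly.
2. Specify one table, by randomised arm, in the existing ITT set. For any adverse event, serious adverse events and adverse events leading to withdrawal, give the number and percentage of patients and the number of events. Add treatment-related events if the CRF records relatedness. Put exact two-sided 95% confidence intervals on the percentages, with no formal test.
3. Under Safety population, say that the ITT set is used in place of N/A.
4. Under Intervention exposure, replace N/A with a reference to the by-arm comparison of sessions attended in the compliance section.
5. List the change with the other amendments. That section shows revisions made during the analysis. If allocation has already been unblinded, the table should be identified as unplanned, as the Introduction requires.

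The cost is a few lines of text and one extra descriptive table. It needs no new data collection, apart from the condition on relatedness, and changes no efficacy analysis.
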